10.5 Trial Discontinuation

The reason for a subject discontinuing from the trial will be recorded in the source documentation and case report form. A discontinuation occurs when an enrolled subject ceases participation in the trial, regardless of the circumstances, prior to completion of the protocol. The Investigator must determine the primary reason for discontinuation. A discontinuation must be reported immediately to the clinical monitor or his/her designated representative if it is due to a serious adverse event (SAE) (see Section 12.3). The final evaluation required by the protocol will be performed at the time of trial discontinuation. The

Investigator will record the reason for trial discontinuation, provide or arrange for appropriate follow-up (if required) for such patients, and document the course of the subject's condition.

Premature termination of this clinical trial may occur because of a regulatory authority decision, change in opinion of the IRB/EC, drug safety problems, or at the discretion of IVERIC bio.

The study will be considered completed when the last subject completes the final study visit.

11 STATISTICAL METHODS

The following summarizes the statistical methods that will be employed in this trial designed to compare the effects of Zimura 2 mg dose against the Sham control arm in patients with geographic atrophy secondary to AMD.

11.1 Study Design

This is a randomized, double-masked, Sham-controlled pivotal study that will obtain evidence regarding the effects of Zimura 2 mg in reducing the mean rate of GA growth over 12 months, when compared with Sham control.

Approximately 400 patients will be randomized at Day 1 in a 1:1 ratio to the following monthly treatment groups:

- Zimura 2 mg
- Sham

Patients receiving monthly Zimura 2 mg will be re-randomized at Month 12 in a 1:1 ratio to the following treatment groups:

- Zimura 2 mg administered monthly from Month 12 - Month 23
- Sham administered at Months 12, 14, 16, 18, 20, and 22, and Zimura 2 mg administered every other month at Months 13, 15, 17, 19, 21, and 23

All patients who were initially randomized to Sham (at Day 1) will continue with monthly Sham injections through Month 23.

All patients will have a final follow up visit at Month 24.

11.2 Endpoints

11.2.1 Primary Efficacy Endpoint

Primary Efficacy Endpoint:

- The mean rate of growth (slope) estimated based on GA area measured by FAF in at least 3 time points: Baseline, Month 6, and Month 12 (square root transformation)

11.2.2 Safety and Tolerability Endpoints

Safety and tolerability endpoints:

- All adverse events reported, whether or not deemed related to the injection procedure or study drug
- All SAEs, whether or not deemed related to the injection procedure or study drug
- Laboratory data (blood: hematology, renal function, hepatic function, and electrolytes; urinalysis)
- Ophthalmic variables (best corrected visual acuity, low luminance best corrected visual acuity, IOP, and ophthalmic examination)
- Vital sign measurements
- 12-lead ECG

11.3 Determination of Sample Size and Statistical Rationale

The sample size for this study is based on recently obtained 12-month results of the OPH2003 pivotal international, multicenter, randomized, double masked, sham-controlled clinical trial that was performed to evaluate the safety and efficacy of Zimura in patients with geographic atrophy secondary to AMD. The prespecified primary endpoint, mean change in GA growth over 12 months, equivalent to the mean rate of GA growth used in this study, was measured by fundus autofluorescence (FAF) based on readings at three time points (Baseline, Month 6, and Month 12) and was calculated using the square root transformation of the GA area. The FAF images were assessed by an independent masked reading center. The reduction in the mean rate of GA growth over 12 months was 0.11 mm ($p = 0.0072$) for the Zimura 2 mg group compared to the Sham control group.

In this Phase 3 trial, the primary analyses will be based on the comparison of the estimated reduction in the mean rate of GA growth over 12 months for Zimura 2 mg group versus the Sham control group. By pre-specification, this study will obtain evidence regarding the effect of Zimura on the mean rate of growth (slope) estimated based on GA area measured by fundus autofluorescence (FAF) in at least 3 time points over 12 months, when compared with Sham (square root transformation). The FAF images will be assessed by an independent masked reading center. The effect of treatment on the square root transformation of the GA area will be assessed using a mixed model for repeated measures model (MMRM) including stratification factors.

A total of approximately 400 patients will be randomized. If the 2 mg dose of Zimura truly provides a 0.11 mm reduction in the mean rate of GA growth over 12 months, then the trial will have 97% power to detect that effect at the two-sided significance level of 0.05. **Statistical**

significance at the two-sided significance level of 0.05 will be achieved for an estimated 0.057 mm reduction in the mean rate of GA growth over 12 months.

11.4 Year 2 Data Analysis

When the 12-month follow-up is complete for the primary analysis, the database will be locked. Post-12 month information will remain fully masked until completion of 24-month follow-up.

11.5 Randomization Procedure

Patients will be centrally allocated to one of the two treatment groups by a dynamic minimization procedure using clinical site in a 1:1 ratio stratified by factors known to be of prognostic importance in AMD:

- Baseline visual acuity < 50 ETDRS letters (20/100 Snellen equivalent) vs \geq 50 ETDRS letters
- Size of Baseline geographic atrophy (< 4 disc areas vs \geq 4 disc areas)
- Pattern of Fundus Auto Fluorescence (FAF) at the junctional zone of GA (None/focal vs banded/diffuse)

Patients initially randomized to Zimura 2 mg at Day 1 will be re-randomized at Month 12 in 1:1 ratio to Zimura 2 mg monthly vs every other month (please see 11.1 Study Design) using the same minimization procedure as for the initial randomization (i.e. using the same factors at Baseline).

Randomization will be performed using an IRT system based on the stratification information above to randomize each subject and assign a treatment arm.

The IRT system will be used to assign masked study kits to patients throughout the duration of the trial. All study medication must be dispensed using the IRT system. At each dispensing visit the IRT system will allocate each study drug kit(s) using the kit number on the label of the study medication kit.

11.6 Masking Procedures

It is the responsibility of the Principal Investigator to ensure that the physician assessing adverse events, the VA examiner, all masked study personnel, and the subject remain masked to the subject's treatment assignment.

To maintain masking, the IRT system will provide instructions as to which kit is to be administered at each dispensing visit. These instructions are located on the IRT confirmation of drug assignments, which is provided for each dispensing visit. This information must be communicated to the unmasked injector and stored with subject's study documentation.

In the case of a rare emergency where, in the Investigator's opinion, unmasking the treatment is necessary to evaluate a further course of action, the Investigator should access the IRT and follow the instructions to initiate unmasking. Any unmasking should be reported to the unmasked contact at the Sponsor immediately.

In the event of an unmasking, the Investigator will be informed of the patient's randomized treatment assignment. Any unmasking information must be stored separately from the patient's study files in a secure location to ensure the treatment assignment remains masked to other site, CRO and Sponsor personnel as required. The IRT system will generate an email notification that does not contain unmasking information, which will be sent to the Investigator and appropriate Sponsor personnel.

11.6.1 Visual Acuity Assessments

Since this is a double-masked study, patients and staff at the investigational site, particularly the visual acuity examiners, will be masked to study treatment. All VA assessments will be performed by the trial refractionist/ophthalmologist, who will be masked to the subject's treatment as well as previous visual acuity assessments. The trial refractionist/ophthalmologist will be supplied only with the subject's most recent protocol refraction.

11.6.2 Injections

Each clinical site is required to have a minimum of two ophthalmologists – the unmasked injector and the masked assessor. The unmasked injector will perform the Zimura/Sham injection as well as the post-injection ophthalmic exam and tonometry measurements. The unmasked injector and designated unmasked assistants (if needed) are not permitted to be involved in the conduct of the study in any other manner and are not to communicate with any other personnel or patients regarding the treatment assignment. The masked assessor will perform all other physician assessments including the relationship of all adverse events to study drug, including those noted by the unmasked injector.

11.6.3 Statistical Analyses

All statistical analyses will be performed by a statistical office independent of the study Sponsor. The Sponsor and the patients will remain masked to treatments until the end of the study, except if safety considerations justify breaking the code for individual patients.

11.7 Analytical Considerations

11.7.1 Analytical Plan

A Statistical Analysis Plan (SAP) will provide the details necessary for the statistical analyses to be explicitly pre-specified prior to unmasking, both at Month 12 and at Month 24. The methods for imputation of post-baseline, missing data will be specified in the SAP.

11.7.2 Significance Levels

The overall two-sided false positive error rate in this trial is 5%.

11.7.3 Descriptive Statistics

Descriptive statistics will be provided on demographic information, treatment administration, Baseline characteristics, and protocol deviations, as well as for selected endpoints at relevant time points. No tests of significance will be carried out to compare treatment groups on Baseline data since the lack of a well-defined sampling context would render corresponding p-values to be uninterpretable.

11.7.4 Efficacy Analysis

The efficacy analysis will be conducted on all randomized and treated patients according to the intention-to-treat principle.

For normal endpoints, treatment groups will be compared through an analysis of variance including stratification factors.

For binary endpoints, treatment groups will be compared through Mantel-Haenszel or Cochran-Mantel-Haenszel χ^2 tests adjusting for stratification factors.

11.7.5 Subset Analyses

The trial is not sized to test for the presence of treatment by Baseline covariate interactions. Thus, true treatment by Baseline covariate interactions likely will not be rigorously established, unless they are quite substantial. In particular, should any subset of patients seem to benefit more or less from therapy than the total population, this will not be taken as reliable evidence of a true treatment by Baseline covariate interaction, given the likelihood that such an observation readily could be due to chance alone. With these caveats in mind, exploratory subset analyses will be performed as descriptive evidence regarding the generalizability of trial results.

11.7.6 Safety Analysis

The safety analysis will be conducted on all patients who had at least one administration of study drug.

Adverse events will be summarized using MedDRA terms. The incidence and severity of adverse events will be listed and grouped by body system.

All laboratory data will be listed and values falling outside normal ranges will be identified. Summary statistics (i.e., mean, median, standard deviation, minimum and maximum) will be presented for all continuous variables.

Summary statistics will be given on the number of patients for whom the trial medication had to be permanently stopped.

12 ADVERSE EVENTS

12.1 Definition of Adverse Events

An AE is defined as follows: Any untoward medical occurrence in a patient or subject including unfavorable and unintended signs, symptoms or disease temporally associated with the use of a medicinal product and which does not necessarily have to have a causal relationship to this treatment.

Adverse events include illnesses with onset during the trial, or exacerbations of pre-existing illnesses. Exacerbation of pre-existing illness is defined as a significant increase in the severity of the illness as compared to the start of the trial and should be considered when a patient requires new or additional treatment for that illness. Lack of or insufficient clinical response or efficacy should not be recorded as an adverse event.

In addition, clinically significant changes in objective findings (e.g., laboratory, ECG, X-ray, physical examination) should also be considered as to whether they are adverse events. The criteria for determining whether an objective finding should be reported as an adverse event are as follows:

1. Associated with accompanying symptoms; and/or
2. Requires medical/surgical intervention; and/or
3. Leads to a change in trial dosing or discontinuation from the trial, significant additional concomitant drug treatment or other therapy; and/or
4. Leads to any of the outcomes included in the definition of a serious adverse event; and/or
5. Is considered to be an adverse event by the Investigator or Sponsor.

Any abnormal test result that is determined to be an error does not require reporting as an adverse event.

12.2 Assessment and Reporting of Adverse Events

Adverse events will be recorded starting after the first dose of study drug and continuing until 30 days after the last dose or until the last follow-up visit required by the protocol, whichever comes later. An adverse event that is ongoing at the last follow up study visit is required to be followed up until the event resolves or stabilizes at a level acceptable to the Investigator and/or Sponsor.

All adverse events spontaneously reported, elicited, or observed by the Investigators will be recorded. The events will be recorded in the source documents and onto the adverse event pages of the case report form, including date of onset and resolution, severity, relationship to trial treatment and determination of whether the event qualifies as a “serious” adverse event (Section 12.3).

Diagnostic and therapeutic non-invasive and invasive procedures, such as surgery, should not be reported as adverse events. However, the medical condition for which the procedure was performed should be reported if it meets the definition of an adverse event. For example, an acute appendicitis that begins during the adverse event reporting period should be reported as the adverse event, and the resulting appendectomy should be recorded as treatment of the adverse event.

The Investigator will take all therapeutic measures necessary for resolution of the adverse

event. Any medication necessary for treatment of the adverse event must be recorded in the subject's source documents and on the appropriate pages of the subject's case report form.

To assist with grading of adverse event severity, the following definitions are provided:

- Mild** = Aware of sign or symptom, but easily tolerated;
- Moderate** = Discomfort enough to cause interference with usual activity;
- Severe** = Incapacitating with inability to work or do usual activity;

Adverse events are assessed as "not related" or "related" to one of the following: (1) the intravitreal injection procedure (including eyelid speculum, anesthetic drops, mydriatic drops, antibiotic drops, povidone-iodine, subconjunctival injection of anesthetic, intravitreal injection of Zimura or anti-VEGF), or (2) related to the study drug (Zimura/sham), or (3) related to anti-VEGF treatment (if administered).

The adverse relationship will be assessed using the definitions below. The investigator will choose either "not related", or chose the most likely cause of the AE (i.e., only one of the relationships noted in the above paragraph may be chosen):

- Not Related** = There is not a reasonable possibility that the adverse event is related to the intravitreal injection procedure, or to the study drug (Zimura/sham), or to the anti-VEGF treatment.
- Related** = There is a reasonable possibility that the adverse event is related to the intravitreal injection procedure or to the study drug (Zimura/sham), or to the anti-VEGF treatment.

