Preclinical, clinical and genetic studies implicate the potential role of the complement cascade in AMD (Bok, 2005; Donoso et al., 2006; Edwards et al., 2005; Hageman et al., 2005; Haines et al., 2005, Liao et al., 2019, Brandstetter et al., 2015, Georgiannakis et al., 2015, Liao et al., 2019, OPH2003). Inhibition of complement activation may potentially slow down or arrest the underlying pathophysiology of macular degeneration. Thus, molecules involved in regulation and inhibition of complement cascade are prime targets for therapeutic intervention in AMD.

Zimura is currently being developed by IVERIC bio for the treatment of GA secondary to AMD and Stargardt disease. Zimura is a pegylated RNA aptamer. It is a potent and specific inhibitor of complement C5. Zimura inhibits C5 cleavage, a central component of the complement

cascade, which plays multiple roles in innate immunity and cell death. Inhibition of this critical step in the complement cascade prevents the formation of key terminal fragments (C5a and C5b) regardless of the initial activation pathway (alternate, classical, or lectin). The C5a fragment plays an important role in inflammasome priming and activation leading to pyroptosis and cell death. C5b is involved in the formation of membrane attack complex (MAC: C5b-9) which also leads to cell lysis and cell death. By inhibiting these C5-mediated activities, one may slow down the progression of retinal cell degeneration and achieve therapeutic benefit in GA secondary AMD.

In this pivotal clinical trial, the safety and efficacy of Zimura 2 mg will be compared to Sham control. This is based on results of the first pivotal clinical trial (OPH2003), in which both Zimura 2 mg and Zimura 4 mg cohorts demonstrated a statistically significant reduction in the mean rate of GA growth over 12 months when compared to their corresponding Sham control cohorts with a similar efficacy, and Zimura 2 mg is administered as a single intravitreal injection vs 2 intravitreal injections for Zimura 4mg.

In the first pivotal trial, treatment with Zimura 2 mg dose, led to a 27.38% reduction in the mean rate of GA growth over 12 months as compared to the corresponding sham control group which was highly statistically significant (p-value = 0.0051). In prior clinical studies, Zimura 2 mg dose was generally well-tolerated with no drug-related AEs, drug-related inflammation, or endophthalmitis. Therefore, the sponsor believes the risk/benefit assessment is favorable.

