Only first year AE data will be included in the following analyses. Treatment Emergent Adverse Events (TEAEs) from the first year will be defined as starting after the first dose of study drug until prior to Month 12 injection. If a Month 12 injection does not exist, the end of the first year is defined as the Month 12 visit (or target of 365.25 days after the first dose if no Month 12 visit) or 30 days after the last injection, whichever is later.

All AEs will be coded using MedDRA™ (version 23.0 update) terms.

- An overview of TEAEs will be provided. A second overview of TEAEs will be provided which displays the overall summary of TEAEs by the categories ‘Study Eye’, ‘Non-Study Eye’, and ‘Non-Ocular’. In addition, the number and percentage of patients with TEAEs will be tabulated for each treatment group and in total by system organ class (SOC) and preferred term (PT). The number and percentage of the subjects who experienced at least one TEAE will be included. Subjects will only be counted once for each preferred term. In case that a subject experienced the same event more than once, the worst severity will be presented.
- Tabular summaries of the following AEs will be provided by SOC and PT:
 - Summary of TEAEs
 - All TEAEs regardless of the relationship to study treatment
 - All TEAEs regardless of the relationship to study treatment with frequency of $\geq 5\%$ in any treatment arm.

CONFIDENTIAL

-
- TEAEs related to study treatment
 - TEAEs related to injection procedure
 - TEAEs by the maximum severity grade
 - TEAEs related to study treatment by the maximum severity grade
 - TEAEs related to injection procedure by the maximum severity grade
 - All Ocular TEAEs by study eye and fellow eye
 - Treatment related Ocular TEAEs by study eye and fellow eye
 - Injection procedure related Ocular TEAEs by study eye and fellow eye
 - Ocular TEAEs (study eye) by the maximum severity grade
 - Treatment related Ocular TEAEs (study eye) by the maximum severity grade
 - Injection procedure related Ocular TEAEs (study eye) by the maximum severity grade
 - TEAEs with high level term of cataract conditions by study eye and fellow eye
 - TEAEs leading to discontinuation of study drug
 - Treatment related TEAEs leading to discontinuation of study drug
 - Injection procedure related TEAEs leading to discontinuation of study drug
 - Ocular TEAEs (study eye) leading to discontinuation of study drug
 - TEAEs leading to death
 - Treatment related TEAEs leading to death

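### Recording only one cause per adverse event lets events that meet the protocol's own definition of drug-related drop out of the drug-related tables

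*Protocol*

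**What the plan says.** Protocol 12.2 gives the investigator a choice between not related and one of three causes: the injection procedure, the study drug, or anti-VEGF treatment if it was given.

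- **Number of causes.** The investigator must "chose the most likely cause of the AE", and "only one of the relationships noted in the above paragraph may be chosen".
- **Standard for relatedness.** The definition begins "There is a reasonable possibility that the adverse event is related to the intravitreal injection procedure or to the study drug (Zimura/sham" and goes on to include anti-VEGF treatment. It asks whether a cause is reasonably possible, not whether it is the most likely one.
- **Procedure category.** Its list of components ends with "subconjunctival injection of anesthetic, intravitreal injection of Zimura or anti-VEGF". The next category is "related to the study drug (Zimura/sham", and anti-VEGF treatment has a third category of its own.
- **Who judges.** Protocol 11.6.2 gives the relatedness judgement to the masked assessor.
- **What is tabulated.** Both SAPs list "TEAEs related to study treatment" and, separately, events related to the injection procedure. The split recurs in the tables by severity and for ocular events, discontinuations, deaths and SAEs (Year 1 SAP, Adverse Events and Serious Adverse Events and Deaths; Year 2 SAP 4.3.2 and 4.3.3). Neither visible list has a table combining drug and procedure, or a table of anti-VEGF-related events.
- **What does not use attribution.** Both SAPs also tabulate all TEAEs and all SAEs whatever their relationship to treatment.

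**The concern.** The protocol applies two standards to one judgement. The definition admits a cause that is reasonably possible; the recording rule keeps only the one thought most likely. For a drug given by intravitreal injection, some ocular events after an injection could plausibly come from the agent, the needle, or both. When such an event is recorded under procedure, a drug relationship that meets the definition is lost from the database and from every table built on it.

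The wording of the procedure category adds to the difficulty. An assessor who reads the injection of Zimura as including the effect of what was injected could place a drug effect there in good faith. The assessor is masked, so the choice between drug and procedure is made without knowing whether Zimura was given.

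What is at stake is how the drug-related tables are read. A reader will take them to hold every event for which a drug contribution was reasonably possible. They hold only those for which the drug was judged the leading cause.

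**Working it through.** The plan states no figure on this point, so there is none to reproduce. The check follows one event through the rules and then bounds the effect.

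**Following an event through the rules**

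1. Suppose an ocular event has a reasonable possibility of drug causation and also of procedure causation. By the definition in 12.2 it is related to both.
2. The recording rule allows one. If the assessor thinks the procedure more likely, the entry is procedure.
3. The event appears in the procedure-related tables and in none of the drug-related ones.
4. If it is recorded under anti-VEGF instead, it appears in neither set, because the visible lists have no anti-VEGF table. Protocol 10.3 allows anti-VEGF and study treatment in the study eye on the same day, so this case can arise.

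**Direction**

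Define:
- D = number of events with a reasonable possibility of drug causation;
- q = share of D that also has a reasonable possibility of procedure or anti-VEGF causation;
- s = share of those shared-cause events that is recorded under the other cause.

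Events recorded as drug-related = D × (1 − q × s).

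Because q and s lie between 0 and 1, the result never exceeds D, and it is below D whenever both are above 0. No event enters the drug category wrongly through this rule, since an event whose most likely cause is the drug also meets the reasonable-possibility standard.

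**Size**

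The documents give neither q nor s. The limits are:
- q = 0 or s = 0: D × (1 − 0) = 100% of D;
- q = 1 and s = 1: D × (1 − 1) = 0% of D.

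As arithmetic only, q = 0.5 and s = 0.5 would give 1 − 0.25 = 75% of D. Nothing in the documents favours that value over any other.

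The formula counts events. The SAP tables count patients once per preferred term, so a patient drops out only when none of that patient's events under the term was recorded as drug-related. The direction is the same and the loss may be smaller.

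**What the recorded data still contain**

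Any event with a reasonable possibility of drug causation should be recorded under one of the three causes. Hence:

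recorded drug ≤ D ≤ recorded drug + recorded procedure + recorded anti-VEGF.

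Both ends can be computed from single-choice data. The planned tables show only the lower end.

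**The case against.** The strongest reply is that safety evaluation in this trial does not rest on attribution. Protocol 11.2.2 defines the AE and SAE endpoints without regard to relatedness. Both SAPs plan all-causality tables by arm, IOP summaries by visit and injection time, and shift tables for anterior chamber cells and vitreous haze before and after injection. The Year 2 SAP adds a summary of events of special interest. The event listings show causality to study medication and injection procedure. All of this stands, and it confines the point to the attributed tables.

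A second reply concerns the category wording. Anti-VEGF also appears inside the procedure list despite having its own category, which suggests that the list means the act of injecting and the other categories mean the agents. That is a reasonable reading, but the text does not state it. Even if it is right, the single-choice rule still removes shared-cause events.

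A third reply is that a most-likely-cause rule works both ways, because events judged mainly drug-related leave the procedure table. That is true of the procedure table, but it does not restore anything to the drug table.

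Some stronger inferences are tempting and are not supported:

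- *That Protocol 4.4 builds this trial's benefit-risk case on these tables.* Its statement, "generally well-tolerated with no drug-related AEs, drug-related inflammation, or endophthalmitis", describes earlier studies.
- *That the earlier pivotal trial's study-eye CNV figures, beside its report of no Zimura-related events, show this rule at work.* The documents do not say which attribution rule that trial used or how those events were coded.
- *That a shift into procedure is hidden by an expected difference from Sham.* The visible text does not describe what the Sham procedure consists of.

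**Conclusion.** The point holds in a limited form. The definition and the recording rule in Protocol 12.2 do not match, so the drug-related TEAE and SAE tables in both SAPs can fall short of what the protocol itself defines as drug-related, and cannot exceed it. The size cannot be estimated from the documents.

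A reader might go further and say that these tables will under-count, or that they are biased low by construction. Neither follows. A shortfall requires at least one shared-cause event to occur and to be recorded under the other cause. It is also a shortfall against the protocol's definition, not against true causation, which no attribution rule observes.

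The conclusion assumes that assessors apply both the definition and the single-choice rule as written, and that redacted text contains no combined table. The all-causality TEAE and SAE comparisons, the IOP and inflammation summaries and the efficacy analysis are untouched.

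**What to change.** **Preferred.** In Protocol 12.2 and on the CRF, replace the single choice with three yes/no judgements per event (study drug, injection procedure, anti-VEGF where given), each held to the reasonable-possibility standard. Not related then means no to all three. State that the procedure category covers the act of injecting, and that effects of the injected agent belong under study drug or anti-VEGF.

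**If the CRF cannot be changed.** Add to both SAPs, for TEAEs and for SAEs, a table of events related to study drug and/or injection procedure, and one of events related to any of the three causes. Footnote the existing drug-related tables to say that they hold only events for which the drug was recorded as the single most likely cause. Base drug-safety statements on the combined tables and the all-causality comparison. The combined tables follow mechanically from recorded data and need no new causality judgement. The Year 2 SAP says the Year 1 analysis has already been done, so its combined tables should be labelled as additions.

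**Cost.** Either a small change to the protocol and CRF, or a few extra tables. With separate judgements the drug-related count may be somewhat higher and will overlap the procedure count, so the two no longer add up. The combined tables include events due to the procedure alone; they bound the drug-related count from above and do not recover it.
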